The study was reviewed as part of the academic requirements for the DClinPsy course that the doctoral student is undertaken. The feedback from the peer review by university academic staff is detailed in the scientific critique document.

PUBLIC & PATIENT INVOLVEMENT

Input will be sought by the service user and carer advisory panel (SUCAP) attached to the Trent DClinPsy programme. Initial input from SUCAP members shaped the formation of the research idea in the early stage of development (January 2021). Additionally, parents/carers have been consulted to check the readability and suitability of the participant information sheet, consent form and interview schedules.

PROTOCOL COMPLIANCE

Accidental protocol deviations may occur at any time. Accidental protocol deviations will be adequately documented on the relevant forms and reported to the Chief Investigator and Sponsor immediately.

Deviations from the protocol which are found to frequently recur are not acceptable, these will require immediate action and could potentially be classified as a serious breach.

DATA PROTECTION AND PATIENT CONFIDENTIALITY

All study staff and investigators will comply with the principles of the General Data Protection Regulation (GDPR) 2016/079 in protecting the rights of study participants with regards to the collection, storage, processing and disclosure of personal information and will uphold the Act's/Regulations core principles.

Each participant will be assigned a participant identification code, for use on study records, other study related documents and the electronic database. Personal data, as defined under the Data Protection Act, will include participant demographics, contact details, signed consent forms, recordings of intervention sessions and

recordings and transcripts of change interviews. Completed measures will not be personally identifiable as an anonymised participant identification code will be used.

Personal data, research data and the linking code will be stored in separate locations. When stored electronically, this will include using encrypted digital files within password protected folders and storage media. Personal information shall be stored separately to research data and will be kept secure, and maintained.

All electronic data will be uploaded on a dedicated secure University of Lincoln web server which uses two factor authentication; access will be restricted by user identifiers and passwords. Paper-based data will be kept in a locked filing cabinet at the University of Lincoln; this will include all data except audio recordings. These recordings will be kept on a password-protected encrypted USB memory stick that will be kept in a locked draw when not being used. When uploaded to the University of Lincoln server, the original audio files will be deleted from the USB. Administrative staff on the Trent DClinPsy will have access to the filing cabinets, but hard copy data will be kept in sealed envelopes. Access to the information will be limited to the study investigators and relevant regulatory authorities. Data analysis will use anonymised data and all data files will be password protected and saved on University of Lincoln servers, which require two-factor authentication. Participants will be given pseudonyms in the write up of the research and any identifiable details will be changed.

Personal data will be stored for 6 months following the end of the study, so that the Chief Investigator may provide participants with a summary of the research (should they wish to receive a copy).

All study data will be stored for 5 years following the end of the study, so that the Chief Investigator may provide participants with a summary of the research (should they wish to receive a copy).

Data generated as a result of this study will be available for inspection on request by the participating physicians, the University of Lincoln representatives, the REC, local R&D Departments and the regulatory authorities.

INDEMNITY

Insurance and indemnity for trial participants and trial staff is covered within the NHS Indemnity Arrangements for clinical negligence claims in the NHS, issued under cover of HSG (96)48. There are no special compensation arrangements, but trial participants may have recourse through the NHS complaints procedures.

The University of Lincoln as research Sponsor indemnifies its staff, research participants and research protocols with both public liability insurance and clinical trials insurance.

ACCESS TO THE FINAL DATASET

The full study documentation and data will be restricted to staff on the research team. The anonymised quantitative dataset may be uploaded and stored on the open access University of Lincoln Repository (ePrints). All documents shall be made available at all times for review by the Chief Investigator, Sponsor's designee and inspection by relevant regulatory authorities.

DISSEMINATION POLICY

The data custodian will be the Chief Investigator on behalf of the University of Lincoln.

This research will be submitted in partial fulfilment of the requirements of the Trent Doctorate in Clinical Psychology. It is the intention to submit the research to a peer-review journal to allow for wider readership. The findings may be disseminated through relevant conferences. Participants will receive a summary of the findings, unless they have opted out on the consent form. All data disseminated will be anonymised.

The total expected duration of the study is 13 months. Planned start date: February 2022 (dependant on approval by ethics committee). Planned thesis submission date: February 2023.

Authorship eligibility guidelines and any intended use of professional writers

The doctoral student will be the primary author on all publications related to this project. The chief investigator and all co-investigators will be co-authors and authorship will be decided based on contribution at the time of publication.

REFERENCES

Achenbach, T. M. (1966). The classification of children's psychiatric symptoms: a factor-analytic study. *Psychological Monographs*, 80(7), 1–37. <https://doi.org/10.1037/h0093906>

Achenbach, T. M. (1978). The child behavior profile: I. Boys aged 6–11. *Journal of Consulting and Clinical Psychology*, 46(1), 478–488.

Achenbach, T. M., & Edelbrock, C. S. (1979). The Child Behavior Profile: II. Boys aged 12-16 and girls aged 6-11 and 12-16. *Journal of Consulting and Clinical Psychology*, 47(2), 223–233. <https://doi.org/10.1037/0022-006x.47.2.223>

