The Brief Problem Monitor (BPM), a short version of the Child Behaviour Checklist (CBCL; Achenbach & Rescorla, 2001), will be used to measure parent-reported child behavioural problems. While both versions have been used extensively in research, the 113 item CBCL is too long to repeat regularly. The BPM is more suitable than the alternative Strengths and Difficulties Questionnaire (SDQ; Goodman, 1997) because of the difference in factor structures; the externalising scale of the BPM is more consistently supported in factor analyses than the five-factor structure of the SDQ which has externalising behaviour represented across three different subscales (McCrory & Layte, 2012).

SECONDARY ENDPOINTS/OUTCOMES

The secondary measures include a parenting practice measure, parental reflective functioning measure, a general wellbeing measure and an ideographic measure to capture parents' perception of the problems and assess any change. A change interview will also be completed with participants.

Parenting practice measure

The Multidimensional Assessment of Parenting Scale (MAPS) uses a two-factor structure that assesses positive (e.g. nurturing, attuned) and negative (e.g. hostile, punitive, critical) parenting practices (Parent & Forehand, 2017). The MAPS takes approximately ten minutes to complete every session, which is a time burden for participants. There are very few alternatives, however, that are shorter and retain adequate psychometric properties. Relying on a self-report measure without observations of parenting is a limitation, although there is evidence to suggest that self-report measures of parenting do correlate with independent observations (Hawes & Dadds, 2006). An observational element is not included because this would impact the feasibility of the study in the given timescale, particularly in the context of the global pandemic. The MAPS will be shortened for repeated measurement purposes. This will be done by taking the top 3 items from the MAPS positive scale and the top 3 from the negative and using that as a proxy process measure. What constitutes 'top' can be established by either face-validity, relative factor loadings of each item derived from the original scale development, or a combination of both.

Parental reflective functioning measure

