Visual analysis is the suggested method of analysing single case design data (Barlow et al., 2009) and consequently will be used to analyse the data resulting from this research. The data will be visually represented on graphs and examined for trends in the data indicating if and when change has occurred across the process measures for the three variables of interest. The data will also be analysed to establish if any changes are reliable and clinically significant. Assessment of reliable change identifies if change is genuine or resulting from measurement error; this will be calculated using the Reliable Change Index (Jacobson & Truax, 1991). If changes prove reliable, they will be analysed for clinical significance (Jacobson & Truax, 1991). The change interviews will be transcribed verbatim by the doctoral student and analysed using framework analysis as outlined by Gale et al. (2013). NVivo will be used to conduct the framework analysis.

Data analysis will be completed by the doctoral student with support from the research supervisors (CI and collaborator). No interim analysis are planned.

STUDY SETTING

The study will be run across two mental health trusts in the East Midlands. The specialist children's services (Child and Adolescent Mental Health Service; CAMHS) within [redacted NHS Trust] will be the primary study site. The CAMHS service consists of four locality teams across the county, all of which work together to form one service. The population being recruited from will be parents/carers of children on the waiting lists for these services. Recruitment will be supported by staff within these services who are aware of the research project and its aims.

The secondary study site will be CAMHS services within [redacted NHS Trust]. Recruitment will only occur in the secondary study site if it has not been possible to recruit sufficient participants from the primary study site. Again, recruitment will be focused on parents/carers of children on the waiting lists for CAMHS services and will be supported by clinical psychologists within CAMHS who are aware of the research project and its aims.

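### The plan does not secure a full MAPS reading before and after the intervention, so reliable change in negative parenting (question 1a) could rest on three unnamed items

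*Combined protocol and SAP*

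**What the plan says.** Secondary Endpoints/Outcomes, Parenting practice measure, first describes the burden: "The MAPS takes approximately ten minutes to complete every session". It remarks that "There are very few alternatives, however, that are shorter and retain adequate psychometric properties", and then decides: "The MAPS will be shortened for repeated measurement purposes". It gives the method: "This will be done by taking the top 3 items from the MAPS positive scale and the top 3 from the negative". The protocol describes the purpose of these six items as "using that as a proxy process measure". The choice of items is left open, since what counts as best "can be established by either face-validity, relative factor loadings of each item derived from the original scale development"; mixing the two approaches is also allowed. No item is named.

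The table Frequency of measure collection has a single MAPS row with ticks at six baseline, six intervention and one follow-up reading. SWEMWBS and PSYCHLOPS have three ticks each: Week 1 Day 1, Week 9 and Week 13.

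Study Regimen has process measures taken at the start of each weekly intervention call, and the complete set of five measures one month after the intervention.

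Data Analysis plans graphs of change "across the process measures for the three variables of interest", and continues: "The data will also be analysed to establish if any changes are reliable and clinically significant". It names the Reliable Change Index, with clinical significance assessed only where change is reliable. It states no form of the MAPS and no pair of readings.

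**The concern.** Question 1a asks whether the intervention reduces negative parenting practices. The Reliable Change Index answers this for one parent by comparing the same score on two occasions, using that score's reliability and SD. Clinical significance also needs a cut-off for that score. Figures for the full negative scale do not carry over to three items picked for this study.

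If the short form is what participants complete at every tick, the SD and cut-off do not exist in advance, and the reliability is at best an estimate. If the full form appears only at follow-up, there is no earlier full score to compare it with. A full baseline reading that was not taken cannot be recovered later, and with three to six participants there is little room to lose one.

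The open item rule adds a smaller problem. If full forms are collected, the three negative items could be settled after scores have been seen.

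**Working it through.** The plan gives no figure to reproduce: it states no MAPS item count, reliability, SD, threshold or cut-off. The check is therefore mainly a comparison of the text.

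**1. Which form at which reading?** The row has 6 + 6 + 1 = 13 ticks. Four allocations are possible:

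- *Short form at all 13.* This follows from the shortening sentence if every ticked reading counts as repeated measurement. Reliable change would then use three negative items.
- *Full form at all 13.* This is the literal reading of the row, which carries the full scale's name. The shortening text would then be redundant.
- *Short form until follow-up, full form at follow-up.* This fits Study Regimen, with process measures at weekly calls and all five measures a month later. The Week 9 reading falls in a weekly call, so it would be short, and the baseline form is not stated. No full score before the intervention is secured.
- *Full form at start, end and follow-up, short form between.* This fits the word proxy and would remove the problem. No text says it.

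Data Analysis does not decide between these. It uses the term process measures for all three variables, including two that are not shortened.

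**2. What the index needs.** The 95% threshold, in SD units of the score used, is 1.96 × √(2(1 − rel)), where rel is the reliability. Both rel and the SD belong to the form used.

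**3. Illustration only.** Assumed, not in the documents: a full negative scale of k = 12 or 18 items with alpha 0.80 or 0.90.

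- Full scale: 1.96 × √(2 × 0.20) = 1.24 SD at alpha 0.80; 1.96 × √(2 × 0.10) = 0.88 SD at alpha 0.90.
- Three average items: mean inter-item r = alpha/(k − alpha(k − 1)), then rel = 3r/(1 + 2r). For k = 12 and alpha 0.80, r = 0.80/(12 − 8.8) = 0.25 and rel = 0.75/1.50 = 0.50.

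The common-scale column uses true-score SD units, 1.96 × √(2(1 − rel)/rel), and assumes that both forms measure the same factor.

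| Score | rel | Threshold, own SD | Threshold, common scale |
|---|---|---|---|
| Full, alpha 0.80 | 0.80 | 1.24 | 1.39 |
| Full, alpha 0.90 | 0.90 | 0.88 | 0.92 |
| 3 average items, k = 12, alpha 0.80 | 0.50 | 1.96 | 2.77 |
| 3 average items, k = 12, alpha 0.90 | 0.69 | 1.54 | 1.85 |
| 3 average items, k = 18, alpha 0.80 | 0.40 | 2.15 | 3.39 |
| 3 average items, k = 18, alpha 0.90 | 0.60 | 1.75 | 2.26 |
| 3 stronger items, r = 0.5 | 0.75 | 1.39 | 1.60 |
| 3 stronger items, r = 0.6 | 0.82 | 1.18 | 1.31 |

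On the common scale, three average items need √(k/3) times the full-scale change: 2.00 for k = 12 and 2.45 for k = 18. But the plan takes top items, not average ones. With r = 0.5 the ratio is 1.15 (1.60/1.39) to 1.73 (before rounding, against alpha 0.90). With r = 0.6 it is 0.94 (1.31/1.39) to 1.41 (before rounding).

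A higher threshold is therefore likely, but its size is not determined by anything in the documents. At the favourable edge the disadvantage disappears.

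**The case against.** Five points can be made for the plan.

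- *The paragraph is not a contradiction.* A reader might infer that ten minutes per session and a six-item form cannot both be meant. The text reads more naturally as a burden followed by its solution, and the remark on shorter alternatives is about other instruments. This stands: the fault is under-specification and an unsplit row.
- *A full form is probably intended somewhere.* The word proxy, and the difference in Study Regimen between process measures and the complete set, both point that way. This stands as a hint, but it does not supply a baseline or end-of-intervention reading. A reader should therefore not infer that question 1a definitely rests on three items.
- *The missing index inputs are not peculiar to the MAPS.* Data Analysis gives no reliability, SD or cut-off for any measure. This stands. What is specific here is the unclear form and the open item rule.
- *Reliability of three items could be estimated.* If items were chosen on published standardised loadings, a composite reliability could be worked out from them. This stands in part, because the SD and the clinical cut-off would still be missing.
- *The illustration proves little.* A reader might take the doubling of the threshold as the finding. It rests on assumed inputs and on average items, so it cannot carry that weight.

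**Conclusion.** The point holds as a gap in specification. No text secures a full MAPS reading before and after the intervention, the form used for reliable change is not stated, and the six short-form items are neither named nor fixed by one rule. Under the short-form-throughout reading, reliable and clinically significant change for question 1a would rest on a three-item score without an established SD or cut-off. Its reliability would probably be below that of the full scale, by an amount the documents do not allow anyone to state.

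The consequence is limited. The question is secondary, visual analysis leads and does not depend on the full form, and the BPM primary outcome is untouched. It is still worth settling before enrolment, because a missing baseline reading is permanent.

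**What to change.** Split the MAPS row of the schedule into full and short, and add text to this effect:

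*The full MAPS will be given at Week 1 Day 1, at the last intervention call (Week 9) and at follow-up (Week 13). Reliable and clinically significant change in negative parenting will be calculated only on the full negative scale between these readings, with the sources of reliability, SD and cut-off named in advance. Six items, named before enrolment by one stated rule, will be used at the remaining readings for visual analysis only. At the full readings the same six items will be scored from the full form.*

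These are the three readings already used for SWEMWBS and PSYCHLOPS, which leaves 13 − 3 = 10 short readings. If the full form is meant at every session, delete the shortening text instead.

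A second full reading at the end of baseline, to show drift, is optional. The baseline phase may run beyond three weeks and stability is judged case by case, so the last baseline call may not be recognised in advance.

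Cost: if the short form is now meant throughout, at most 3 × 10 = 30 minutes per participant, on the protocol's own figure of about ten minutes. The full form at every reading would take 13 × 10 = 130 minutes. One drawback is that the six items sit inside a longer form at three readings, which may shift their scores. This should be borne in mind when reading the graphs.
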